5.0	5 Jun., 2018	Updated the treatment of cohort 1. Updated the original treatment for cohort 1 (at least four cycles of SHR-1210 combined with capecitabine and oxaliplatin sequenced by SHR-1210 monotherapy as maintenance treatment) to the following: SHR-1210 + capecitabine + oxaliplatin for 4-6 cycles, followed by SHR-1210 + apatinib in the treatment of the subjects without disease progression. Based on the above revisions, relevant contents including the title of the study, were updated: The title was updated to "An Open-Label, Multi-Center, Phase II Study of Anti-PD-1 Antibody SHR-1210 Plus Capecitabine and Oxaliplatin Sequenced by SHR-1210 with Apatinib Mesylate or Apatinib in Patients with Previously Untreated Advanced or Metastatic Gastric (GC) or Gastroesophageal Junction (GEJ) Cancer"; The study objectives were updated to "Primary objective: To evaluate the efficacy of the sequential therapy of SHR-1210 combined with capecitabine and oxaliplatin or SHR-1210 combined with apatinib mesylate as the first-line therapy for advanced or metastatic gastric (GC) or gastroesophageal junction (GEJ) cancer"; Secondary objective: "To evaluate the safety of the sequential therapy of SHR-1210 combined with capecitabine and oxaliplatin or SHR-1210 combined with apatinib mesylate for the treatment of advanced or metastatic gastric (GC) or gastroesophageal junction (GEJ) cancer". According to the latest CDE requirements on drug safety, relevant contents in the study were updated: a) AEs: AEs are recorded from the date of signing informed consent to the end of the safety follow-up (90 days after the last dose) or the start of a new anti-cancer therapy. b) Death caused by the symptoms and signs of PD will be reported as an SAE. c) "Definitely related", "possibly related" and "unlikely related" and "indeterminable" are all listed as adverse drug reactions. d) The collection and follow-up duration of AE/SAE are reinforced (see section 7.4.1). e) The CFDA and the National Health and Family Planning Commission have changed to other names but the GCP and Provisions for Drug Registration have not been updated yet. Therefore, the reporting of SAEs was updated: "The SAE must be reported to the relevant regulatory authorities, the sponsor, and the ethics committee within 24 hours of knowing of the event. The sponsor's email address for safety data is: [contact] ."
-----	--------------	--

6.0 8 Aug., 2018

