7.3.2 Criteria for causality between adverse events and study drugs

AEs include all unexpected clinical manifestations. All the AEs occurring after the signing of the ICF must be reported as an AE, regardless of whether the AEs are related to the study drugs, whether the subject is allocated to the investigational drug group, and whether the subject has been administered with the drug. Any discomforts complained by the subject or changes in objective laboratory measurements during the treatment period should be truthfully recorded. The severity,

duration, measures taken, and the outcome of AEs should also be documented. The study physician shall assess the relationship between the AE and the study drugs by considering the time sequence between the administration of study drug and the occurrence of AE, characteristics and toxicology of the study drug, concomitant medications, underlying diseases, medical history, family history, as well as dechallenge and rechallenge. The causality assessment will be provided using the following five categories "definitely related, possibly related, unlikely related, definitely unrelated, and indeterminable". Events that are assessed to be "definitely related", "possibly related", "unlikely related", and "indeterminable" will be listed as adverse drug reactions. When calculating the incidence of adverse events, the total of these four categories will be used as the numerator and the total number of subjects for safety evaluation will be used as the denominator.

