8.1 Statistical Analysis Plan

The primary objective of this study is to evaluate the efficacy of the sequential therapy of SHR-1210 combined with capecitabine and oxaliplatin (cohort 1) or SHR-1210 combined with apatinib mesylate (cohort 2) as a first-line treatment for advanced or metastatic Gastric (GC) or gastroesophageal junction (GEJ) cancer. The primary efficacy endpoint is ORR.

Detailed summaries and methods of statistical analyses for the data collected from the study shall be included in the statistical analysis plan (SAP), which shall be finalized and filed by the sponsor. The SAP should be revised accordingly if there are any changes to the study protocol that may have a major impact on the SAP, as determined by the sponsor or principal investigator. Relevant content in statistical analysis plan that is relevant to this protocol may be revised. However, if revised content involves the main and/or key factors of the protocol (such as the definition of endpoints or their analysis), such content in the protocol will be revised.

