8.4.3 Safety analysis

The safety analysis is based on the safety set (by actual treatment received). According to Hengrui's Standard Reporting Procedures, safety will be only summarized using descriptive statistics, including but not limited to the following. The specific analysis is described in the statistical analysis plan:

- ◆ Subject disposition and populations;
- ◆ Subjects' basic characteristics (including demographics, life history, medical history, and medication history);
- ◆ Discontinuations;
- ◆ Summary of adverse events (of all causes and treatment-related);
- ◆ Incidence and severity of adverse events (of all causes and treatment-related);
- ◆ Summary of serious adverse events;
- ◆ Causality analysis of adverse events;
- ◆ Occurrence of abnormal laboratory measurements, vital signs, and ECG data.

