## 2 PROTOCOL AMENDMENT

Added overall survival (OS), time to objective response (TTOR), and subgroup analysis as exploratory efficacy analysis to provide guidance for subsequent phase III clinical studies

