In the TEAE summary table, AE occurring after the study drug treatment will be analyzed by MedDRA system organ class (SOC) and preferred term (PT), and descriptive statistics will be provided by frequency and percentage. The summary table contains the number of subjects experiencing at least one TEAE, TEAEs leading to treatment withdrawal, SAEs, TEAEs related to each study drug, and CTCAE Grade  $\geq 3$  treatment-related TEAE, along with CTCAE grades. After study drug treatment, each TEAE, SAE, TEAE of special interest, immune-related TEAE, and possible liver injury event, along with CTCAE grade, in each cohort will be summarized by SOC and PT, and each treatment-related TEAE and SAE related to study drugs will be summarized by SOC and PT. Immune-related AE will also be summarized by immune-related category and PT. The incidence of AE is calculated based on the number of subjects having an AE, instead of the number of AE episodes. For TEAE occurring after the start of study treatment, causality with study drugs consists of definitely related, possibly related, and indeterminable; if causality is missing, the TEAE will be considered drug-related for analysis. TEAE with CTCAE grade missing will be counted as missing.

TEAE of special interest includes the following:

- Grade  $\geq 3$  infusion reaction;
- Grade  $\geq 2$  diarrhea/colitis, uveitis, and interstitial pneumonia;
- Other Grade  $\geq 3$  immune-related AE;
- Grade 4 amylase or lipase increased.

Each AE, TEAE leading to dose interruption or modification, TEAE leading to treatment withdrawal, severe TEAE, and death will be listed.

For immune-related TEAE (classified by immune-related TEAE), the descriptive summary of the number and percentage of subjects have received corticosteroids or immunomodulators, received immunomodulators, received corticosteroids (further divided into systemic and topical administration), and received high-dose corticosteroids (defined as at least one dose or daily dose of  $\geq 40$  mg prednisone or equivalent; further divided into systemic and topical administration), and the starting dose and duration of high-dose corticosteroids will also be provided. The dosage of different hormonal drugs will be converted into the equivalent dose of prednisone according to the following formula: 0.75mg of dexamethasone = 5 mg of prednisone = 4mg of methylprednisolone = 20mg of hydrocortisone = 0.8mg of betamethasone.

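### SAP 11.4.1 leaves events rated unlikely related out of drug-related TEAEs, although protocol 7.3.2 counts them as adverse drug reactions

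*SAP*

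**What the plan says.** Protocol 7.3.2 has the investigator rate causality on five levels and then groups four of them: "Events that are assessed to be 'definitely related', 'possibly related', 'unlikely related', and 'indeterminable' will be listed as adverse drug reactions". Only *definitely unrelated* falls outside. The section continues: "When calculating the incidence of adverse events, the total of these four categories will be used as the numerator", with the subjects evaluated for safety as denominator. According to the protocol's version history the grouping came in with version 5.0, and it stands in the current text.

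Protocol 8.4.3 plans summaries of "Incidence and severity of adverse events (of all causes and treatment-related"), so all-cause and treatment-related results are separate outputs. It leaves the detail to the SAP.

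SAP 11.4.1 gives a shorter list for TEAEs: "causality with study drugs consists of definitely related, possibly related, and indeterminable". It then adds: "if causality is missing, the TEAE will be considered drug-related for analysis". Incidence is counted by subject, not by episode.

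SAP section 2, where changes relative to the protocol are recorded, mentions only efficacy: "Added overall survival (OS), time to objective response (TTOR), and subgroup analysis as exploratory efficacy analysis". No other part of the SAP brings *unlikely related* back.

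**The concern.** Both texts are current, and they build the numerator of a treatment-related rate differently. Two analysts, one following each document, could report different rates from the same data. For rated events the difference can go only one way: dropping a category cannot raise a count, so any change makes the treatment-related profile look more favourable.

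The outputs affected in SAP 11.4.1 are related TEAEs overall and by drug, related grade 3 or higher TEAEs, related SAEs, and related TEAEs leading to discontinuation, interruption or dose modification. Attribution already matters in this trial. The version 6.0 entry in the protocol history reports four apatinib-related SAEs among 11 patients on the combination, and a dose change followed.

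The all-cause AE and SAE tables, the secondary safety endpoint as worded in protocol 2.2, and the response thresholds in SAP section 5 do not use causality and are not at stake.

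**Working it through.** The documents state no treatment-related rate for this trial, so there is no figure to reproduce. The check compares the two sets of categories and then works out what one subject is worth.

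**Step 1. The categories side by side**

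| Recorded causality | Protocol 7.3.2 | SAP 11.4.1 |
|---|---|---|
| Definitely related | counted | counted |
| Possibly related | counted | counted |
| Indeterminable | counted | counted |
| Unlikely related | counted | not counted |
| Definitely unrelated | not counted | not counted |
| Missing | no rule | counted |

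Protocol set minus SAP set is *unlikely related*. SAP set minus protocol set is missing causality.

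**Step 2. Does the SAP sentence define relatedness?** It does not say so outright. It cannot be a description of the rating scale, because it omits *definitely unrelated* as well. The clause that follows assigns missing ratings to the drug-related group, which makes sense only if the listed ratings form that group.

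**Step 3. Which incidence does protocol 7.3.2 mean?** Its numerator sentence speaks of adverse events in general. Read literally, it would remove *definitely unrelated* events from all AE incidence, which conflicts with the all-cause summaries in protocol 8.4.3. I therefore read it as the incidence of adverse drug reactions.

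**Step 4. Direction.** With no missing causality, the SAP set is contained in the protocol set, so for any row the SAP count is at most the protocol count. It is strictly lower when at least one subject qualifies for that row only through *unlikely related* events. This works row by row. A subject with a possibly related grade 2 event and an *unlikely related* grade 3 event is in the any-grade related row under both definitions, but in the related grade 3 or higher row only under the protocol's.

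**Step 5. Size per subject.** The shift in a row is k/n. Here k is the number of subjects who qualify only through *unlikely related* events, and n is the size of the safety set. The actual n is not known in advance. As illustrations I use the design sizes (43 and 55) and the sizes inflated for 10% non-evaluable subjects: 43/0.9 = 47.8, so 48, and 55/0.9 = 61.1, so 62, as in protocol 8.2. The documents do not give k, so the values 1 and 5 are assumptions.

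| k | Cohort 1, n = 43 | Cohort 1, n = 48 | Cohort 2, n = 55 | Cohort 2, n = 62 |
|---|---|---|---|---|
| 1 | 2.3 points | 2.1 points | 1.8 points | 1.6 points |
| 5 | 11.6 points | 10.4 points | 9.1 points | 8.1 points |

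These figures hold for whole-cohort rows. SAP 11.4.1 also summarises cohort 1 by treatment stage, and only subjects without progression move on to SHR-1210 plus apatinib. If those rows use the subjects who entered that stage as denominator, n is smaller and each subject weighs more.

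**The case against.** The strongest reply is that the two texts do not use the same term. Protocol 7.3.2 says what is listed as an adverse drug reaction, while protocol 8.4.3 and the SAP speak of treatment-related events. No sentence equates them, and the protocol leaves the details of the safety analysis to the SAP. The conflict therefore rests on two readings, those in steps 2 and 3. That is fair as a statement of what is inferred. But 7.3.2 is the only rule in the protocol that groups causality ratings. The synopsis also plans an analysis of adverse drug reactions, and the SAP has no separate table for them. As written, no planned SAP incidence table uses the protocol's four-category numerator.

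A second reply is that the version 5.0 grouping may have been meant for safety reporting, since its neighbours in the log are collection and reporting rules. This is possible, and the regulatory requirement behind it cannot be seen here. The point therefore rests on the current text of 7.3.2, which gives a numerator and a denominator for an incidence.

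Third, protocol 8.1 lets the SAP differ and calls for a protocol revision only "if revised content involves the main and/or key factors of the protocol". This stands in part. A three-category definition is not wrong in itself; what cannot stand is an undeclared difference from the protocol.

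Fourth, the effect may be small. The any-grade related row probably moves least, since most subjects should qualify through another event. The protocol's background rates of adverse drug reactions with apatinib alone (78.72% and 92.05%) point that way, but they come from another dose and population and cannot size the effect here. The missing-causality rule can also offset part of the loss, though only by chance, since it acts on unrated events.

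**Conclusion.** The concern holds. SAP 11.4.1 counts a narrower set of rated events as drug-related than protocol 7.3.2 does, and neither document declares or explains the change. The direction is certain among rated events: treatment-related rates under the SAP are equal to or lower than under the protocol. The size cannot be known from the documents and may be zero, with the per-subject weights as worked out above for whole-cohort rows. The conclusion assumes that the SAP sentence defines relatedness and that the numerator sentence in 7.3.2 refers to adverse drug reactions. This is a discrepancy that should be settled before database lock; it has no bearing on the primary response result.

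**What to change.** In SAP 11.4.1, add *unlikely related* to the drug-related definition, so that the four rated categories match protocol 7.3.2. State the rule for missing causality separately, as a conservative SAP addition, and report how many events it affects. Show the three-category version as a supportive table. The causality analysis that protocol 8.4.3 lists, for which the SAP specifies no table, would be a natural place to show the share of *unlikely related* ratings.

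If the sponsor prefers three categories as the main definition, declare that in SAP section 2 and decide under protocol 8.1 whether 7.3.2 must be revised. Either route should be completed before database lock.

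The cost is one SAP sentence, one derivation flag and one supportive table. Data collection does not change. Treatment-related rates may look slightly less favourable.

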Once a patient given intravenous injections of steroids shows a sustained clinical improvement, the patient can switch to an equivalent dose of oral corticosteroids (e.g., prednisone) by the time or before the dose of steroid injections starts to be gradually reduced. When switching to oral corticosteroids with an equivalent dose in the lungs and liver, it should be considered that the bioavailability of oral corticosteroids is relatively low.

5. Management Principles for Skin Adverse Events

[figure not shown]
Rash Grade (NCI CTCAE v4)	Handling	Follow-Up
Grade 1-2 Coverage \leq 30% body surface area (BSA)	
♦ Symptomatic treatment (e.g., antihistamines, topical steroids);♦ Continue the immunotherapy according to the study protocol.	
If symptoms persist for > 1-2 weeks or recur:
 
♦ Consider skin biopsy;♦ Delay the immunotherapy according to the study protocol;♦ Consider intravenous administration of 0.5-1.0 mg/kg/d methylprednisolone or an equivalent orally administrated dose. Once improved, reduce the dose of steroids for at least 1 month and consider prophylactic antibiotics to prevent opportunistic infections, and resume immunotherapy according to the study protocol. 
If it is aggravated:
 
♦ Provide treatment according to the method for grade 3/4 situations.
Grade 3-4 Coverage \geq 30% body surface area (BSA); or life-threatening results	
♦ Delay or discontinue the immunotherapy as per the study protocol;♦ Consider consultation with the Department of Dermatology;♦ Intravenous administration of 1.0-2.0 mg/kg/d methylprednisolone or an equivalent dose via intravenous injection.	
If it is improved to Grade 1:
 
♦ Reduce the dose of steroids for at least 1 month and add prophylactic antibiotics to prevent opportunistic infections;♦ Resume the immunotherapy according to the study protocol.

Once a patient given intravenous injections of steroids shows a sustained clinical improvement, the patient can switch to an equivalent dose of oral corticosteroids (e.g., prednisone) by the time or before the dose of steroid injections starts to be gradually reduced. When switching to oral corticosteroids with an equivalent dose in the lungs and liver, it should be considered that the bioavailability of oral corticosteroids is relatively low.

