If one subject experiences one AE and receives two or more hormones during the presence of the AE, the starting dose of the hormone used first will be involved in the statistics of starting doses (i.e., the starting dose(s) of subsequent hormone therapy/therapies will not be involved in the statistics of starting doses). Then, the cumulative duration of the use of multiple hormones (time overlapping of hormone therapies should be avoided in the calculation) will be summarized as the duration of dosing. If one AE category (such as the category of immune-related AE) contains more than one AE (by PT), this AE category will be treated as one AE when being summarized. When the initial dose is summarized, if the dosing frequency of hormones is more than once a day, it will be converted into a single daily dose before being summarized. When the duration of dosing is summarized, if the end date of hormone drug treatment is unknown, it will be imputed with the start date of the last dose of the hormone drug treatment.

Corrective treatment, site, maximum diameter, incidence of hemorrhage, and incidence of infection will also be summarized for reactive capillary endothelial proliferation.

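### The SAP's multi-hormone rules carry no dose or route limit, so the reported start of high-dose corticosteroids can be an earlier dose below the SAP's own 40 mg cut-off, and the reported duration can include that earlier course

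*SAP*

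**What the plan says.** SAP 11.4.1 (Adverse event) gives a descriptive summary of steroid use for immune-related TEAEs. A subject counts as having high-dose corticosteroids after at least one dose or daily dose of 40 mg or more of prednisone or its equivalent. These counts are "further divided into systemic and topical administration". The SAP then adds that "the starting dose and duration of high-dose corticosteroids will also be provided".

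The derivation rules follow directly in the same section:

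- They apply when a subject with one AE "receives two or more hormones during the presence of the AE".
- For the start, "the starting dose of the hormone used first will be involved in the statistics of starting doses". The starting doses of later hormones are expressly left out.
- For duration, the SAP takes "the cumulative duration of the use of multiple hormones", with overlapping time counted once.
- If an AE category contains more than one preferred term, "this AE category will be treated as one AE when being summarized".

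No other starting-dose statistic is described in this section, so these rules serve the high-dose summary. They do not repeat the 40 mg condition or the route split.

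**The concern.** The statistic is named for high-dose treatment, but its derivation is triggered by any two hormones and takes the first of them at whatever dose it was given. If the first hormone was below 40 mg and a different, later one reached the cut-off, the subject enters the table because of the later course but is described by the earlier one. The table can then show a high-dose start that fails the SAP's own definition, and a duration that includes days before high-dose treatment began.

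Protocol Appendix 4 makes the sequence plausible. For Grade 2 diarrhea/colitis it allows a lower-dose steroid, which may be oral, and moves to the Grade 3-4 approach if symptoms worsen or persist after several days of oral steroid. If the oral drug is not methylprednisolone, that is two hormones. Category pooling extends the effect: a lower-dose hormone given for one preferred term can set the start for a high-dose course given for another term in the same category.

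The two statistics are meant to show how much immunosuppression immune-related events required. Where the error occurs, it lowers the start and lengthens the duration.

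**Working it through.** **Inputs**

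- Cut-off: 40 mg prednisone equivalent (SAP 11.4.1).
- Conversion: 4 mg methylprednisolone = 5 mg prednisone (SAP 11.4.1), a factor of 5/4 = 1.25.
- Grade 2 diarrhea/colitis: methylprednisolone 0.5-1.0 mg/kg/d or an oral equivalent; Grade 3-4: 1.0-2.0 mg/kg/d IV; taper of at least 1 month (Protocol Appendix 4).
- Assumptions: body weight 60 kg, two different drugs, 5 days on the first.

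The plan states no figure to reproduce here beyond the cut-off and the conversion.

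**Step 1. Can a first course fall below the cut-off?**

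Prednisone equivalent = mg/kg × weight × 1.25. At 0.5 mg/kg/d:

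| Weight (kg) | Prednisone equivalent (mg/d) |
|---|---|
| 50 | 31.25 |
| 55 | 34.4 |
| 60 | 37.5 |
| 64 | 40.0 |
| 70 | 43.75 |

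The break-even weight is 40 / (0.5 × 1.25) = 64 kg; lighter subjects are below the cut-off. At 1.0 mg/kg/d it is 40 / 1.25 = 32 kg, so a first course at the upper end of the range will nearly always qualify and cause no problem.

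**Step 2. Apply the rule as written.**

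A 60 kg subject takes an oral steroid equivalent to 0.5 mg/kg/d methylprednisolone (37.5 mg) for 5 days, then IV methylprednisolone 1 mg/kg/d: 60 × 1.25 = 75 mg.

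- The subject qualifies as high-dose because of the 75 mg course.
- Start as written: 37.5 mg, which is below 40 mg. The first qualifying course starts at 75 mg.
- Duration as written: the qualifying treatment plus 5 days.

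**Step 3. Separate the rule's effect from the taper.**

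For illustration, assume 7 days of IV treatment and then a 30-day linear oral taper from 75 mg:

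- As written: 5 + 7 + 30 = 42 days.
- Qualifying courses, taper included: 7 + 30 = 37 days.
- Days at 40 mg or more: 21.

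The missing dose limit accounts for 42 − 37 = 5 days. The other 37 − 21 = 16 days depend on whether duration means the whole course or only the days at or above the cut-off, which the SAP does not say.

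**Step 4. Topical first (rash).**

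Appendix 4 lists topical steroids for Grade 1-2 rash, with systemic steroids to be considered if it persists. Assume 14 topical days before the same 37 days. The rule gives 14 + 37 = 51 days if routes are pooled, and 37 on the systemic line if the route split applies. The SAP does not say which.

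**The case against.** The best defence is context. The rules come straight after the sentence on high-dose starting dose and duration, so hormones may mean only the high-dose ones. On that reading nothing is wrong. It is possible, but the SAP does not state it, and a programmer following the text would not be led to it.

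Other objections stand and limit the point:

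- The rule needs two hormones. Escalation within one drug, such as methylprednisolone from 0.5 to 2 mg/kg, does not clearly trigger it; the SAP gives no rule for that case. A reader might infer a fourfold understatement (37.5 against 150 mg at 60 kg) from such a sequence, but it does not follow from this text.
- A reader might infer that topical doses and days certainly enter the figures. Because the high-dose counts are split by route, the same split may be intended for start and duration.
- A reader might infer that duration is overstated two- or threefold. Most of such a gap is taper. The definition, which needs only one qualifying dose or daily dose, is compatible with reporting a whole course, so counting only days at 40 mg or more is a choice of quantity and not a correction.
- A reader might infer that this is frequent. Appendix 4, which is offered only as a reference, starts Grade 3-4 events and Grade 2 pneumonitis at doses above 40 mg prednisone equivalent at 60 kg.

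**Conclusion.** The point holds as a gap in a stated derivation rule. Read literally, SAP 11.4.1 can tabulate a high-dose start below its own 40 mg definition, and a duration that includes an earlier lower-dose course. This happens when a lower-dose hormone precedes a different, high-dose hormone for the same AE or AE category.

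In the example the start is reported as 37.5 mg instead of 75 mg, half the qualifying dose, with 5 extra days. That rests on an assumed 60 kg weight, two different drugs and 5 days on the first. At 0.5 mg/kg/d the start falls below the cut-off only under 64 kg. The topical part is uncertain.

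The documents give no basis for counting affected subjects, and they do not support a claim that the table is wrong for a particular share of them. The number of subjects counted as receiving steroids does not change, nor do ORR or the stage decisions. This is a minor point, about the derivation and not about how steroids should be given.

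**What to change.** In SAP 11.4.1:

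1. Apply the first-hormone and cumulative-duration rules only to hormone courses that meet the 40 mg definition. The start is the dose at the first qualifying course or day for that AE or AE category.
2. Apply the systemic/topical split already used for the high-dose counts to both statistics. The dose conversion can stay as it is, since the SAP also counts high-dose topical use.
3. Label duration as either the whole qualifying course including taper or only the days at 40 mg or more. Either is acceptable if stated. Total corticosteroid duration can go on a separate line if wanted.
4. Say how escalation within a single hormone is handled, since no rule covers it now.

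The cost is a few sentences of SAP text and programming on concomitant-medication records that the protocol already collects. No treatment rule changes.
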